6.6 Early Termination Visits

All subjects that decide to leave the study early or are asked to by the investigator will be strongly encouraged to continue follow-up visits, but early termination visits are not planned.

7 Study Evaluations and Measurements

7.1 Medical Record Review

- Date of birth
- Address
- Contact information (telephone / email)
- Hospital admission date and date of brain injury
- Past medical history as it relates to PPA and other neurologic conditions, cardiac status, and surgery
- Results of neuroimaging studies and dates, including MRI and/or CT exams
- Current and past medications or therapies

7.2 Physical Examination

Should subjects report new complaints or a change in their neurologic/language status, an examination will be performed by the PI or other neurologist working on the project.

7.3 Laboratory Evaluations

Participants will be asked to undergo high quality brain imaging via MRI at the University of Pennsylvania. We will obtain 3D T1-weighted MPRAGE images at a 1mm isotropic spatial resolution in order to provide anatomical data. Multiband resting-state fMRI data will be collected for ~10 minutes, at a resolution of 3x3x3 mm³(TR = 0.5s, TE = 30ms, 230x230 mm² FoV, 128x128 acquisition matrix). Diffusion Spectrum Imaging (DSI) scans will sample 257 directions using a Q5 half shell acquisition scheme with a maximum b value of 5000 and an isotropic voxel size of 2.4mm. (Parameters: TR = 11.4s, TE = 138ms, 51 slices, FoV (231,231,123 mm,6 B0 images).

7.4 Pregnancy Testing

There is no known risk to a mother or fetus from tDCS or MRI, but due to the fact that the safety of the technique in pregnant women has not been fully studied, pregnant women are excluded from the study. If the female subject is of child-bearing age, a urine pregnancy test will be performed before the first tDCS sessions.

7.5 Other Evaluations, Measures

The following battery of language tasks will be administered prior to treatment and at 6 weeks and 12 weeks (& 24 weeks in crossover) after the completion of tDCS: (1) The Western Aphasia Battery (WAB; Shewan & Kertesz, 1980) samples a number of different language functions and

CONFIDENTIAL

generates a summary score between 0-100 (Aphasia Quotient, AQ), interpretable as general aphasia severity. The WAB will be administered on two occasions prior to treatment to obtain a stable baseline. Word and non-word repetition tests from the Moss Psycholinguistic Aphasia Database (MAPPD; Dell et al, 1997; Sobel, Brecher, & Schwartz, 2006) will be used to further assess lexical and post-lexical phonological encoding. Word repetition will also be used to quantify instances of consonant distortion, prosodic alteration, and other features of speech apraxia. The Pyramids and Palm Trees test (Picture version; Howard & Patterson, 1992) will be used to assess core semantic memory. (5) The Communication Confidence Rating Scale for Aphasia (Babbitt, Cherney, & Halper, 2008) will be administered to assess changes in quality of communication in daily life. Spontaneous Speech as an indicator of functional communication will be assessed with the Cinderella story (Stark, 2010). The Linguistics Test for Reception of Grammar (LTROG, Bishop, 1989) will be administered to assess grammatically comprehension of speech and written language. Finally, 2 pre-treatment baselines will be obtained on the stimuli used for CILT. We note that the baseline sessions may require more than one day to complete.

7.6 Efficacy Evaluations

No interim analyses for efficacy are planned, as previous work suggests that the maximal benefit is likely to be obtained at the 12 week endpoint and there is no additional risk to the subject after the tDCS is completed.

7.7 Safety Evaluations

Although we consider the risk to be extremely low, subject safety will be assessed throughout the course of the study by asking subjects if they have experienced adverse effects from the interventions. As any adverse effects of tDCS are likely to occur at the time of stimulation, we will ask all subjects before and immediately after tDCS if they note any symptoms of concern. This will be documented for each subject at each stimulation session.

8 Statistical Plan

8.1 Primary Endpoint

The primary endpoint will be overall change in WAB-AQ between the baseline visit and the 12 week follow-up visit (real compared to sham tDCS).

8.2 Secondary Endpoints

Change in accuracy on additional language assessment given over baseline & follow-up visits will serve as secondary outcomes. As well as any changes in fMRI data.

8.3 Sample Size and Power Determination

To calculate power, we started from an ambitious but realistic estimate of the population available at the participating recruitment sites. We intend to recruit 62 subjects, although 25 subjects will be adequate to detect a difference between real and sham stimulation within each group (alpha = 0.05; power = 0.8). Although our historical attrition rate has been 15%, we will conservatively anticipate a 25% attrition rate and will therefore enroll 31 subjects in each PPA variant arm.

CONFIDENTIAL

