To date, only a handful of studies have investigated the utility of tDCS in persons with PPA. An early case study of one individual with naPPA demonstrated improvements in auditory word-picture identification, picture naming, oral word reading, and word repetition in the absence of speech therapy after five days of tDCS applied over the left posterior region and the left inferior frontal gyrus (LIFG) (Wang et al., 2013). Cotelli and colleagues (2014) found that 10 sessions of tDCS over the left dorsolateral prefrontal cortex combined with individualized speech therapy led to improved picture-naming in a small sample of subjects with naPPA who received tDCS compared to sham stimulation; the benefit lasted up to 12 weeks post-stimulation. More recently, a double-blind, sham-controlled cross-over design study involving 12 subjects with svPPA found that bilateral tDCS to the temporal poles transiently improved semantic accuracy in persons with svPPA (Teichmann et al., 2016).

Our lab conducted a pilot study in a small cohort of subjects with PPA (n=6; 4 lvPPA; 2 naPPA) to determine the feasibility of delivering ten sessions of tDCS to the left hemisphere with follow-up testing immediately after, six weeks, and twelve weeks after stimulation. In order to engage the language network during tDCS, subjects performed an unstructured language task during stimulation in which they verbally narrated wordless children's books. We saw significant improvement in measures of speech production, grammatical comprehension, and semantic processing, which persisted up to twelve weeks post-stimulation (Gervits et al., 2016). We next conducted a randomized, sham-controlled crossover pilot study of the same stimulation approach with follow-up testing two and twelve weeks after stimulation. In a cohort of 7 subjects (1 lvPPA; 6 naPPA), we found beneficial effects of stimulation on global language performance (McConathey et al., 2017). Attrition in these studies was low (~15%).

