4.5 Total Number of Subjects and Sites

We intend to enroll up to 62 subjects: 31 naPPA/lvPPA; 31 svPPA

Subjects will be stimulated and tested in HUP or Perelman School of Medicine buildings. Depending on the availability of rooms, four testing sites may be employed: Neurology out-patient offices in the Perelman Center, Neurology out-patient offices on Ravdin 2, laboratory of [name] (Gibson 3), or laboratory of [name] (Goddard). The tDCS device is portable and no special equipment is required.

Additionally, if it is requested by the participant, we may conduct study sessions in the participant's home. In order to be eligible for home visits, patients must live within 40 miles, or approximately one hours, of the University of Pennsylvania. Ultimately, the discretion for eligibility of home visits will be up to the Principal Investigator, in order to best effectively and efficiently manage the lab's resources. If participants do qualify for home visits, they will be required to come to the lab for their first stimulation session. If the patient does not experience any adverse events during that stimulation session and if the other requirements are met, then all subsequent stimulation sessions would be conducted in the participant's home. Again, we would like to stress that this is only an option, not a requirement, which participants may choose if it is more convenient for them. Study visits not requiring the use of tDCS may be conducted at the participant's home if this situation proves to be more convenient for the participant.

4.6 Vulnerable Populations:

Children, fetuses, neonates, or prisoners are not included in this protocol.

Although not directly targeted, mentally disabled persons, economically or educationally disadvantaged persons, and/or employees or students of the University of Pennsylvania will not be denied enrollment and any special protections and/or additional safeguards will be undertaken

CONFIDENTIAL

in order to protect the rights and welfare of these subjects from coercion or undue influence as appropriate.

5 Study Intervention (Study drug, device, biologic, vaccine, food etc.)

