8.4 Statistical Methods

8.4.1 Treatment Effect on Language Performance

A linear mixed-effects model will be used to determine whether the change in performance induced by tDCS + mCILT for subjects in each PPA variant group differs significantly from that induced by sham stimulation, covarying for age, sex, education and disease duration at time of study if they are imbalanced between the two groups at baseline. The mixed model will include a fixed effect for sequence, period, treatment, and the interaction between treatment and period. A random intercept term will be included in the mixed-effects model to account for correlations from repeated outcome measures. Additional analyses will examine change in other language battery tests, and exploratory analysis will examine baseline aphasia severity as a predictor of response.

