8.5 Subject Population(s) for Analysis

The population that will be subject to analysis will be the full randomized with crossover population. Subjects that are non-compliant with treatment/crossover will be encouraged to continue with follow-up and these measurements will be enter into analysis.

9 Safety and Adverse Events

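### Section 8.3: enrolling 31 per variant does not cover the anticipated 25% attrition; about 23 would complete, not the 25 tied to 80% power

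*Combined protocol and SAP*

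**What the plan says.** Section 8.3 (Sample Size and Power Determination) builds the enrolment target in three steps.

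- The number needed: "25 subjects will be adequate to detect a difference between real and sham stimulation within each group (alpha = 0.05; power = 0.8").
- Past experience: "Although our historical attrition rate has been 15"%. Section 1.1.2 reports about the same rate for the team's two PPA pilot studies, of 6 and 7 subjects.
- The allowance and its result: "we will conservatively anticipate a 25% attrition rate and will therefore enroll 31 subjects in each PPA variant arm".

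Section 4.5 carries the result forward: "We intend to enroll up to 62 subjects: 31 naPPA/lvPPA; 31 svPPA".

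Two later sections bear on what attrition would cost. Section 8.4.1 plans a linear mixed model for the treatment effect in each variant group: "A random intercept term will be included in the mixed-effects model to account for correlations from repeated outcome measures". Section 8.5 defines who is analysed: "The population that will be subject to analysis will be the full randomized with crossover population". It adds that measurements from non-compliant subjects who stay in follow-up are used.

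**The concern.** The 31 is presented as the consequence of applying a cautious 25% attrition rate to a requirement of 25. If a quarter of 31 subjects are lost, fewer than 25 remain, so the figure does not do what the sentence says.

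A reader relies on 8.3 to judge whether each variant comparison keeps its stated power under the planned losses. The allowance actually ends at about 19%. Measured from the historical 15%, the stated margin is 25 − 15 = 10 percentage points and the real one is 19.4 − 15 = 4.4. Between 19.4% and 25% attrition, each variant group ends below the number that 8.3 links to 80% power.

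**Working it through.** **Inputs**

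- Adequate number per variant group: 25, at alpha 0.05 and power 0.8 (8.3)
- Anticipated attrition: 25% (8.3)
- Historical attrition: 15% (8.3; about 15% in 1.1.2)
- Enrolment: 31 per variant, 62 in total (8.3 and 4.5)
- Effect size, SD and sidedness: not given

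**Step 1. Where 31 may come from.** Adding 25% to the required number gives 25 × 1.25 = 31.25, which matches 31 after rounding down. Section 8.3 shows no formula, so this is an inference. That form inflates the base by a quarter; it does not allow for losing a quarter of those enrolled.

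**Step 2. Enrolment that retains 25.** The required enrolment is n/(1 − d), where d is the attrition rate: 25/0.75 = 33.3, rounded up to 34. Check: 33 × 0.75 = 24.75 and 34 × 0.75 = 25.5.

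**Step 3. What 31 delivers.**

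| Attrition | Expected completers from 31 |
|---|---|
| 15% | 31 × 0.85 = 26.35 |
| 19.4% | 25 (break-even, 1 − 25/31 = 0.194) |
| 22.6% | 24 (1 − 24/31 = 0.226) |
| 25% | 31 × 0.75 = 23.25 |

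**Step 4. Illustrative power with completers only.** I took a paired t test at alpha 0.05 (noncentral t, n − 1 degrees of freedom) and back-solved the effect from an assumed power at a reference n.

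| Assumption | Power at n = 23, two-sided | Power at n = 23, one-sided |
|---|---|---|
| 25 gives exactly 80% | 76.3% | 76.8% |
| 24 already gives 80% | 78.1% | 78.4% |
| 23 already gives 80% | 80% | 80% |

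In the last row, 25 would give 83.5% (two-sided) or 83.0% (one-sided), so 25 would carry two subjects of margin.

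**Step 5. What partial data might recover.** I used a simplified version of the mixed model: intercept, sequence, period and treatment; equal sequences; between-period correlation r; and 23.25 subjects with both periods. The treatment-by-period term in 8.4.1 is left out, because with two sequences and two periods it cannot be estimated alongside the other terms (rank 4 for 5 parameters). The 31 − 23.25 = 7.75 dropouts supply first-period data in none, half or all cases. The table gives the equivalent number of complete pairs.

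| Dropouts with period-1 data | r = 0 | r = 0.4 | r = 0.5 | r = 0.8 |
|---|---|---|---|---|
| None | 23.25 | 23.25 | 23.25 | 23.25 |
| Half (3.875) | 25.04 | 24.29 | 24.11 | 23.59 |
| All (7.75) | 26.57 | 25.14 | 24.80 | 23.85 |

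If 25 complete pairs give exactly 80% (two-sided), this range of 23.25 to about 26.6 pairs corresponds to about 77% to 83% power. The documents give neither r nor the timing of dropout; both are assumed.

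**The case against.** Four points can be made for the plan.

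- **25 is never called a number of completers, and adequate may include margin.** This is true as far as the wording goes. But the section moves from 25, through attrition, to a larger enrolment, which only makes sense if 25 is the number to be retained. The per-variant reading is supported by 8.3 itself and by the analysis within each variant group in 8.4.1. Any margin in 25 is not stated.
- **At the team's own 15%, 31 is enough.** This stands. It limits the consequence but does not make 31 follow from 25%, which is the rate 8.3 uses. The 15% also rests on small pilots.
- **Attrition need not mean lost data.** Section 8.5 analyses the full randomized population, and sections 6.6 and 9.7 encourage subjects who leave early or stop treatment to continue follow-up. This also stands: Step 5 shows that recovery could run from none to complete. Full recovery needs dropouts to supply first-period data and the between-period correlation to be low, and 8.3 claims no credit for either.
- **The power figures are back-solved and the mixed-model check is simplified.** Correct. They illustrate the likely size; they do not measure the plan. The arithmetic finding rests on neither.

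**Conclusion.** The concern holds, and it is minor. Under the stated 25% attrition, 31 enrolled leaves about 23 completers per variant against the 25 given as adequate, and 31 protects 25 only up to about 19%. This rests on reading 25 as a per-variant number to be retained, which 8.3 implies but does not say outright.

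The shortfall is about two subjects per variant at 25% and nil at or below 19.4%. Its effect on power cannot be fixed from the documents. If 25 gives exactly 80%, a completers-only paired test loses about 3 to 4 percentage points. If 25 carries margin, or if the mixed model draws enough from partial data, the loss could be smaller or absent.

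**What to change.** Keep 31 per variant and replace the last sentence of 8.3 with wording such as:

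> Enrolling 31 subjects per variant retains 25 completers up to about 19% attrition, which covers the historical 15%. At 25% attrition about 23 are expected to complete, fewer than the 25 stated as adequate for 80% power.

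The sponsor should add the power at 23 completers, using the effect size and SD behind its figure of 25.

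The cost is one reworded sentence and one short recalculation by the sponsor. Enrolment, section 4.5 and the study summary do not change. The stated attrition allowance becomes less favourable, about 19% instead of 25%.

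The alternative is to enrol 34 per variant, 68 in total and six more than 62. That would also reconcile the sentence, but I do not propose it: 31 already covers the historical rate, and 8.3 itself describes its estimate of the available population as ambitious.

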8.4 Statistical Methods

8.4.1 Treatment Effect on Language Performance

A linear mixed-effects model will be used to determine whether the change in performance induced by tDCS + mCILT for subjects in each PPA variant group differs significantly from that induced by sham stimulation, covarying for age, sex, education and disease duration at time of study if they are imbalanced between the two groups at baseline. The mixed model will include a fixed effect for sequence, period, treatment, and the interaction between treatment and period. A random intercept term will be included in the mixed-effects model to account for correlations from repeated outcome measures. Additional analyses will examine change in other language battery tests, and exploratory analysis will examine baseline aphasia severity as a predictor of response.

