2.1 Primary Objective

- To determine the efficacy of tDCS + mCILT in improving language performance in persons with PPA compared to sham tDCS + mCILT.

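### The objective, endpoint and Study Summary imply one real-versus-sham contrast in all PPA, but sections 8.3 and 8.4.1 power and test two variant groups at 0.05 each, and nothing says which is primary or what counts as success

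*Combined protocol and SAP*

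**What the plan says.** Three places describe a single question.

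- Section 2.1 sets the primary objective as the efficacy of tDCS with mCILT in "improving language performance in persons with PPA compared to sham tDCS + mCILT".
- Sections 3.2.1 and 8.1 define one primary endpoint, the change in WAB-AQ to 12 weeks, real against sham, with no split by variant.
- The Study Summary describes mixed models comparing real with sham on WAB-AQ change, again with no split.

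Two places describe a question for each variant.

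- Section 8.4.1 applies the mixed model to whether the change "for subjects in each PPA variant group differs significantly from that induced by sham stimulation". The fixed effects listed are sequence, period, treatment and treatment by period. Variant does not appear, alone or with treatment.
- Section 8.3 states that "25 subjects will be adequate to detect a difference between real and sham stimulation within each group (alpha = 0.05; power = 0.8"). It adds that "we will conservatively anticipate a 25% attrition rate and will therefore enroll 31 subjects in each PPA variant arm". Section 4.5 gives the same split: "We intend to enroll up to 62 subjects: 31 naPPA/lvPPA; 31 svPPA".

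No alpha split, testing order or success rule is given for efficacy. The only multiplicity control is the FDR threshold for the hub-score regression in section 8.4.3. Section 8.5 names the full randomized population for analysis and does not mention variant.

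**The concern.** The trial has three candidate efficacy tests: pooled, naPPA/lvPPA and svPPA. The plan does not rank them. An analyst could decide after seeing the data which one answers the primary objective, and whether one positive variant group is enough.

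The choice affects the conclusion even when the treatment works. With the planned 80% power in each group, at least one group is positive in 1 - 0.2² = 96% of trials and both are positive in 0.8² = 64%. In about a third of trials the verdict would therefore turn on a rule that has not been written down.

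The comparison that matches the objective, and uses all participants, appears only in the Study Summary. The methods section does not specify it and the sample-size section does not power it.

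**Working it through.** **Inputs.** Alpha 0.05 and power 0.8 within each group, 25 subjects needed, 25% attrition and 31 enrolled per variant (section 8.3). Two groups with no participants in common (section 4.5). Sidedness is not stated; two-sided is assumed. No effect size or SD is stated; section 8.3 says that "we started from an ambitious but realistic estimate of the population available at the participating recruitment sites". Each test is treated as a paired comparison, which ignores the few degrees of freedom spent on period and sequence.

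**The plan's own figure.** The 25 cannot be reproduced without an effect size, but it can be solved backwards.

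- Normal approximation: (1.960 + 0.842)/√25 = 0.560 for the standardized paired difference d_z.
- Noncentral t: d_z = 0.584 two-sided (0.512 if one-sided). The two-sided value is used below.

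**Completers.** 31 × 0.75 = 23.25, so about 23 per group and 46 in all.

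**Error if neither variant responds.**

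- Either group counts, two-sided: 1 - (1 - 0.05)² = 9.75%. A simulation of 200,000 trials gave 9.7%.
- Either group counts, only errors favouring real tDCS: 1 - (1 - 0.025)² = 4.94%. This becomes 9.75% if the stated 0.05 is one-sided.
- Both groups must be positive, two-sided: 0.05² = 0.25%.
- Two separate claims, each about its own variant: 5% each.

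**Precision of the pooled test (noncentral t, two-sided 0.05).**

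- Effect detectable with 80% power: d_z 0.611 in one group of 23, and 0.422 pooled over 46.
- Power at d_z 0.584, equal in both variants: 76% in one group of 23, 97% pooled over 46 and 98% pooled over 50.

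**If only one variant responds.** With equal groups the pooled effect halves to 0.584/2 = 0.292. The noncentrality is 0.292 × √46 = 1.98, so the pooled test has about 49% power.

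The chance of declaring an effect in the responding variant (d_z 0.584, simulated; unadjusted by noncentral t) is:

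| Completers per group | Unadjusted | Holm | Gated on pooled test |
|---|---|---|---|
| 23 | 76% | 66% | 46% |
| 25 | 80% | 70% | 50% |

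**If both variants respond equally** (25 per group), power for a given variant is about 80% unadjusted, 80% gated and 77% with Holm.

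**The case against.** A reader might infer that no pooled test is planned anywhere. The documents do not support that. The Study Summary describes an unsplit comparison, the endpoint is a single contrast, the analysis population is everyone randomized, and section 8.4.1 speaks of one model. What is supported is a conflict between these places and the per-variant wording of sections 8.3 and 8.4.1.

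A reader might also take 9.75% as the plan's false-positive rate. It is not a property of the plan. It needs a rule that either positive group is enough, which is nowhere stated, and it counts errors in both directions. If the variants are separate questions with separate claims, each keeps its 5%.

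There is also a scientific case for testing by variant. Section 8.4.3 contrasts variants with pathology at the stimulation site with those whose pathology is remote from it. Section 1.1.3 says the therapy suits speech-production deficits, and section 8.4.2 examines variant as a predictor of response. Different effects by variant are therefore anticipated, and in that case a pooled test loses power and gating the variant tests on it loses more. This objection stands against treating a pooled gate as free. It does not remove the need to say which analysis is primary, and it does not change the objective, which asks about PPA as a whole.

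**Conclusion.** The concern holds as an unresolved conflict over the primary analysis. Objective, endpoint and summary point to one contrast; the methods and sample size specify two. Neither a ranking nor a success rule is given.

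Depending on the unstated rule, the two-sided error of an efficacy claim for PPA when neither variant responds lies anywhere from 0.25% to 9.75%. These figures assume independent two-sided tests at 0.05.

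Making the pooled contrast primary matches the stated question and, if both variants respond equally, raises power from 76% (one group of 23) to about 97% (46 completers). That gain rests on the back-solved d_z of 0.584 and on equal effects. If only one variant responds, the pooled test has about 49% power, and this should be stated openly when the choice is made.

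**What to change.** In section 8.4.1, make the treatment effect pooled over both variant groups, with variant as a fixed effect, the single primary test at two-sided 0.05. Align the Study Summary and sections 8.1 and 8.3 with it. In section 8.3, state the effect size and SD assumed, the sidedness, and the power of the pooled test at the expected number of completers.

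Report the effect in each variant as secondary, with a treatment-by-variant term so that a difference between variants is estimated directly.

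If confirmatory claims for each variant are wanted, the sponsor should choose one of two procedures before unblinding and restate power.

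- **Gate on the pooled test, then test each variant at 0.05.** This costs almost nothing if both variants respond, but detection falls from 76% to about 46% at 23 completers per group if only one does.
- **Holm across the two variants.** This costs a few points if both respond, and gives about 66% if only one does. Keeping 80% power at 0.025 in each group would need 31 completers per group, or 31/0.75 = 41.3, so 42 enrolled.

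The pooled primary test itself needs only a change of wording, with no added participants or visits.

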3.1.4 Follow up Phase

There will be an immediate, 6-week and 12-week follow-up following both the initial component. The crossover component will have an additional 24 week follow-up. The full language assessment will be repeated at each follow-up. Subjects will also be asked to complete an MRI scan at the immediate and 12 week follow-ups. Depending on the patients stamina, language assessments may take three visits.

The follow-up visit may be conducted via tele-assessment.

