3.2 Study Endpoints

3.2.1 Primary Study Endpoints

The primary endpoint will be overall change in WAB-AQ between the first baseline visit and the 12 week follow-up (real tDCS compared to sham tDCS).

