6.4.6 Visits 19-35 (Crossover)

Participants will crossover into the second half of the study after the 12 week follow-up. Visits 18 & 19 will serve as Baseline and then all study procedures will exactly match the first half of the study. The crossover will include an additional follow-up visit at 24 weeks.

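### A single participant random intercept can understate the standard error of the real-versus-sham comparison, depending on which WAB baseline and how many follow-ups enter the model

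*Combined protocol and SAP*

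**What the plan says.** Section 8.4.1 asks "whether the change in performance induced by tDCS + mCILT for subjects in each PPA variant group differs significantly" from that under sham. The fixed effects are listed: "The mixed model will include a fixed effect for sequence, period, treatment, and the interaction between treatment and period". The only statement about correlation is "A random intercept term will be included in the mixed-effects model to account for correlations from repeated outcome measures". There is no participant-by-period effect, residual covariance structure, visit term or degrees-of-freedom method. The section does not say whether a participant contributes one change per period or one for each follow-up.

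The endpoint is fixed at 12 weeks, but its starting point is worded in two ways: "overall change in WAB-AQ between the first baseline visit and the 12 week follow-up" in 3.2.1 and "overall change in WAB-AQ between the baseline visit and the 12 week follow-up visit" in 8.1. Section 7.5 adds "The WAB will be administered on two occasions prior to treatment to obtain a stable baseline" without saying whether the two values are averaged.

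For the crossover, 6.4.6 states "Visits 18 & 19 will serve as Baseline". In Figure 1, Visit 18 is an MRI. The first WAB form is at Visit 17, which is also the period-1 12-week follow-up, and the second is at Visit 19. On follow-ups, 3.1.4 states "There will be an immediate, 6-week and 12-week follow-up", with a further 24-week visit after the crossover.

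**The concern.** A participant random intercept implies one common, non-negative correlation among all of a participant's changes. Two features of this design can break that.

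- **Shared Visit 17.** If the Visit 17 WAB is the period-1 outcome and also the period-2 baseline, its measurement error enters the first change with a plus and the second with a minus. The two changes can then be negatively correlated. A variance bounded at zero cannot represent this, so the model treats them as independent.
- **Several follow-ups per period.** All changes within a period share that period's baseline error, so they are more alike than changes from different periods. A single intercept cannot separate the two levels of correlation.

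In both cases the standard error of the real-versus-sham contrast is too small. At stake are the confidence interval and p-value of the primary comparison, for which 8.3 sets alpha at 0.05 within each variant group. With several follow-ups and no visit term, the treatment coefficient also averages over visits and no longer estimates the 12-week effect named as primary.

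**Working it through.** **The plan's own figure.** Section 8.3 gives 25 participants per group for 80% power at alpha 0.05. It states no effect size, SD or correlation, so 25 cannot be reproduced. It can only be inverted: for a paired contrast, two-sided, (1.960 + 0.842)/√25 = 0.56 SD (0.58 with the noncentral t). This says nothing about the covariance.

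**Inputs.** From the documents: alpha 0.05, equal allocation to the two sequences, 25 per variant group, and 31 × 0.75 = 23.25, so about 23 after the planned attrition. Assumed, because not given: two-sided test, independent visit error with SD 1, SD τ of a participant's true change per period from 0 to 1.5 error SDs, and REML with the intercept variance bounded at zero. In a 2x2 crossover, treatment-by-period is aliased with sequence (the listed design matrix has rank 4 of 5). The figures are therefore for the within-participant treatment contrast, with that interaction left out.

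**One 12-week change per period: correlation ρ of the two changes** (τ = 0, 0.5, 1, 1.5)

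- Visit 17 shared: ρ = (τ² − 1)/(τ² + 2) = −0.50, −0.33, 0.00, +0.29
- Two WABs averaged for each baseline: ρ = (τ² − 0.5)/(τ² + 1.5) = −0.33, −0.14, +0.20, +0.47
- Visit 19 alone: ρ = τ²/(τ² + 2) = 0, +0.11, +0.33, +0.53
- Both changes from the very first baseline: ρ = +0.5 or more

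When ρ is negative and the model sets it to zero, the model SE is 1/√(1 − ρ) of the true SE. At ρ = −0.5 this is 1/√1.5 = 0.816, and the large-sample error is 2 × [1 − Φ(1.96/√1.5)] = 0.110.

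**Three changes per period: example with Visit 19 as baseline and τ = 0.** Each change has variance 2. The covariance is 1 within a period (6 pairs) and 0 across periods (9 pairs), so the fitted common covariance is about 6/15 = 0.4 and the residual variance 2 − 0.4 = 1.6. The model variance of the difference between period means is 2 × 1.6/3 = 1.067. The true variance is 2 × (1 + 1/3) = 2.667. The SE ratio is √(1.067/2.667) = 0.632, and the error is 2 × [1 − Φ(1.96 × 0.632)] = 0.215.

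**Simulated type I error, no treatment effect** (20,000 trials per setting, 25 per group; 23 per group is almost the same)

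| Baseline for period 2 | One change: τ = 0 | 0.5 | 1.0 | 1.5 | Three changes per period |
|---|---|---|---|---|---|
| Visit 17 (shared) | 11.0% | 9.4% | 6.1% | 4.9% | 20.5–24.9% |
| Mean of two WABs | 9.1% | 7.1% | 5.3% | 4.8% | 13.7–18.6% |
| Visit 19 only | 6.0% | 5.6% | 5.1% | 4.7% | 17.7–22.3% |
| Very first baseline | 4.9–5.2% over all τ | | | | 4.9–19.0% |

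The small excess near ρ = 0 arises because about half of the trials produce a negative sample correlation, which is set to zero. If true change is independent between a participant's two periods, so that it does not raise ρ, the shared-Visit-17 error with one change stays at 8.0–10.6% (24 per group). With three changes, a shared Visit 17 and added participant-by-period variation, it reaches 29.7%.

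**After the fix.** Testing the within-participant contrast of period means gives 4.6–5.3% in every setting.

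**The case against.** A reader might infer that the planned test necessarily exceeds 5%, or that 11% or 25% is this trial's error rate. The documents do not support that.

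- With one change per period, a random intercept handles any clearly positive correlation. Error is about 5% if both changes start from the very first baseline, which is one way to read 3.2.1, and 5–6% with Visit 19 alone.
- The 11% needs Visit 17 as the sole period-2 baseline, which no section states, and no variation in true change. The disease is progressive, one group pools naPPA with lvPPA, and both periods include mCILT. Stable differences between participants would push the correlation upward.
- Several follow-ups per period is the less natural reading for the primary test. Sections 3.2.1 and 8.1 both fix 12 weeks, and the missing visit term suggests one change per period. Two periods already count as repeated measures.
- Software that allows a negative intercept variance would remove the one-change problem.
- The fixed effects in 8.4.1 cannot all be estimated. If sequence were dropped under reference coding, the treatment coefficient would be the period-1 between-participant contrast, and these figures would not apply.

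All of this stands, and it limits the point to a conditional risk. It does not remove it. The plan rules out none of the inflated readings, names no software, and leaves the baseline and the number of rows open. A reader might also infer that Visit 17 must not serve as a baseline. That does not follow either, because an unrestricted covariance deals with its reuse.

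**Conclusion.** The concern holds as a conditional one. The covariance in 8.4.1 can understate the standard error of the real-versus-sham contrast. Whether it does depends on the period-2 baseline, on the number of changes entered per period, and on variance components that the documents do not give.

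With one 12-week change per period, the reading closest to the stated endpoint, the excess ranges from none to about 6 percentage points (11% against 5%). With three changes per period from a period-specific baseline it is about 9 to 20 points (14–25% against 5%), and the estimand also shifts away from 12 weeks. All figures rest on the assumed variances, on a variance bounded at zero and on the within-participant contrast. Should-fix: the size is uncertain, but a specification that holds the nominal level under every reading is available for a change of wording.

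**What to change.** 1. In 8.4.1, state that the primary test uses one 12-week WAB-AQ change per period. Specify an unstructured 2x2 covariance for the two changes and a small-sample degrees-of-freedom method. For participants with both periods this is equivalent to comparing the period-1 minus period-2 contrast between the two sequences, which may be named instead.
2. If other visits are entered, add visit and treatment-by-visit terms and a participant-by-period random effect, and test the 12-week contrast.
3. Reconcile 6.4.6, Figure 1, 3.2.1 and 8.1 on which WAB or WABs form the baseline of each period, and say whether paired values are averaged. With the unrestricted covariance, reuse of Visit 17 no longer affects type I error, so avoiding that visit is optional.

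The cost is wording in the statistical section and a matching clarification in the protocol sections. No visit, assessment or participant is added. The confidence interval may be wider where the planned model would have understated it.
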